1.2. Study Title

Extension study in a cohort of adult patients with SARS CoV2 infection requiring hospital admission and received treatment with plitidepsin in the APLICOV-PC study.

1.3. Protocol code

E-APLICOV-PC/ AV-APL-A-003-21

1.4. Drug Research Ethics Committee (CEIm)

Drug Research Ethics Committee of HM Hospitales

1.6. Investigational product

Plitidepsin

1.7. Clinical Trial Phase

APLICOV-PC proof-of-concept study follow-up.

1.8. Study objective

Evaluate the incidence of post-COVID morbidity and characterise the complications profile in patients who participated in the APLICOV-PC study.

1.9. Study design

Multi-site extension study of the APLICOV-PC clinical study follow-up.

The plitidepsin doses considered in this trial include the three doses specified in the APLICOV-PC study:

- 1.5 mg of plitidepsin administered as a 1.5-hour infusion, once a day for 3 consecutive days (total dose 4.5 mg).
- 2.0 mg of plitidepsin administered as a 1.5-hour infusion, once a day for 3 consecutive days (total dose 6.0 mg).
- 2.5 mg of plitidepsin administered as a 1.5-hour infusion, once a day for 3 consecutive days (total dose 7.5 mg).

1.10. Disease under study

COVID-19 infection or SARS CoV2 infection.

1.11. Endpoints

Incidence of post-COVID-19 complications.

1.12. Study population and total number of patients

The main objective of the study is to evaluate the incidence of post-COVID morbidity and characterize the complications profile in patients who participated in the APLICOV-PC study.

The maximum number of patients who can participate in the trial is limited to 42.

1.13. Inclusion and exclusion criteria

1.13.1. Inclusion criteria

Patient who participated in the APLICOV-PC study treated with plitidepsin and who gives their consent.

1.13.2. Exclusion criteria

There are no exclusion criteria for this study.

1.14. Study schedule

Inclusion start date: 10/2021

Inclusion end date: December 2021

The study will end with the last procedure performed on the last patient. It is estimated that all procedures will have ended in the month after the inclusion of the first patient in the study.

3. ABBREVIATIONS

Abbreviation	Term
AE	Adverse Event
AEMPS	Spanish Agency for Medicines and Health Products
AUC	Area Under the Curve
CEIm	Drug Research Ethics Committee
CK	Creatine-phosphokinase
CRF	Case Report Form
EC	European Community
ECG	Electrocardiogram
ECO	Ecocardiogram
eCRF	Electronic Case Report Form
eEF1A	Eukaryotic elongation factor
EU	European Union
FEV1	Forced expiratory volume in 1 second
FVC	Forced vital capacity
GCP	Good Clinical Practice
GOT	Glutamic oxaloacetic transaminase
GPT	Glutamate-pyruvate transaminase
HR	Heart rate
IC50	Inhibitory concentration 50
IC90	Inhibitory concentration 90
ICH	International Council for Harmonisation
ID	Identification number
LDH	Lactate dehydrogenase
mMRC	Modified Medical Research Council
MUGA	Multigated acquisition scan
PaFi Ratio	Ratio of partial pressure arterial oxygen and fraction of inspired oxygen.
PR	PR interval
Q1	First quartile
Q3	Third quartile
QT	QT interval

Abbreviation	Term
RR	Respiratory rate
SAE	Serious Adverse Event
SAFI	Ratio of percutaneous oxygen saturation to the fraction of inspired oxygen.
SaO ₂	Oxygen saturation
WHO	World Health Organisation
WMA	World Medical Association

4. STUDY CHARACTERISTICS

4.1. Study identification

Protocol code:

E-APLICOV-PC/ AV-APL-A-003-21

Title:

Extension study in a cohort of adult patients with SARS CoV2 infection requiring hospital admission and received treatment with plitidepsin in the APPLICOP-PC study.

4.2. Study phase

APLICOV-PC proof-of-concept study follow-up.

4.3. Description of the investigational product

Plitidepsin.

5. JUSTIFICATION AND OBJECTIVES

5.1.Introduction

COVID-19

In December 2019, the World Health Organisation received information on a group of cases of pneumonia of unknown aetiology. The cause of this pneumonia was identified as a new virus in the Coronaviridae family (SARS CoV2) and the clinical picture associated with the virus has been named COVID-19.

In January 2020 the first case was reported in Spain and in mid-February the first patient died of it. The growth of confirmed cases has not stopped since then.

On 10 September 2021, the Coordination Centre for Health Alerts and Emergencies of the Ministry of Health reported that in Spain there have been 4,907,461 cases and 85,290 deaths [1].

COVID-19 is currently a public health emergency. The onset of a virus unknown until the end of 2019 has made it necessary to take measures taking into account the existing scientific knowledge with similar viruses and past situations.

[figure not shown]
APLICOV-PC study

The APLICOV-PC proof-of-concept study of plitidepsin [2] has fulfilled the primary safety objective. The characterised range of doses, of 1.5, 2.0 and 2.5 mg/day x 3 consecutive days, confirms a positive therapeutic index in the study's target population (adult patients with COVID-19 infection requiring hospital admission), as well as a good tolerance to the treatment, and the absence of any differences in the level of safety between the 3 evaluated doses.

It is believed that the framework of pharmacological intervention proposed in the indicated group of patients could impact the natural course of the disease, based on:

- The dose range proposed according to the PK/PD model, anticipated that supra-pharmacological concentrations would be reached in distal anatomical compartments.
- The in-vivo biodistribution of plitidepsin confirms that key organs in SARS CoV2 are exposed to therapeutic concentrations (Fig. 1).

[figure not shown]
Figure 1. AUC_{0-t} of the Total Radioactivity in SD Rats (Both Sexes) after a Single Administration of an I.V. Bolus dose of ¹⁴C₁-Plitidepsin A 1.2 mg/m² (0.2 mg/Kg).

*For plasma AUC_{0-t}, t=72 and 48 h in male and female rats, respectively.

- The terminal half-life exceeding 30 hours supports a pharmacologically valid model of exposure, administering the medication over 3 consecutive days. With all the three dosage levels used (1.5 mg, 2.0 mg and 2.5 mg), plasma concentrations above IC₅₀ were obtained throughout the treatment period and remained above IC₉₀ for most of the administration interval. The accumulation after three repeated administrations is minimal.

Figure 2. Total plasma concentration profiles vs. plitidepsin time predicted for the administration schedule and doses used in the APLICOV-PC study.

The horizontal lines represent the total plasma concentrations associated with lung concentrations equivalent to IC50, IC90 and 3xIC90 *in vitro*.

The APLICOV-PC proof-of-concept study has validated the proposed hypothesis in terms of impact on viral load (Fig. 3), full recovery / discharge from hospital rapidly induced (Fig. 4) and very relevant impact on lymphocyte reconstitution and other relevant inflammatory parameters (Fig. 5).

Figure 3. Effect of Plitidepsin and Remdesivir on viral load.

[figure not shown]

Figure 4. Time until discharge from hospital by dose and category (FDA)

[figure not shown]
[figure not shown]

Figure 5. Inflammatory markers in APLICOV-PC patients: Effect of the Dose in Subjects with Moderate COVID-19 according to the FDA.

Therefore, these results generated in the APLICOV-PC proof of concept study are deemed to be compatible with consideration as a tangible post-COVID clinical benefit, in which reference is made to the prevention/minimisation of

complications related to the SARS CoV2 infection. Also, it should be highlighted that 87% of the patients had a moderate to severe illness when they entered the APLICOV-PC study and, on day 15, 82% of the patients had already been discharged.

The last patient was included in the APLICOV-PC study in November 2020. Therefore there is already an extensive margin of time for follow-up of almost 12 months, which justifies this study's approach.

The complications following SARS CoV2 infection represent a medical challenge. The evolutionary process following SARS CoV2 infection is critical in terms of the patient's quality of life, the emergence/persistence of morbidities, and social and pharmacoeconomic impact [3-5]. The potential impact of plitidepsin in controlling the sequelae arising from the SARS CoV2 infection is deemed sufficiently clinically relevant to justify the creation of this study.

Post-COVID 19 Syndrome

SARS CoV2 infection is a systematic process that goes beyond affecting the respiratory tract. COVID-19 complications and sequelae are very varied and increasingly frequent and better documented. Post-COVID sequelae occur after a severe SARS CoV2 infection in patients who required hospitalisation admission. They are generally a consequence of structural damage to different organs by the infection itself and/or associated complications. Various studies point to the sequelae of this infection not only restricting the respiratory apparatus: sequelae have also been recorded in the cardiovascular system, in the kidneys and in the central and peripheral nervous system [6-11]. Psychiatric and psychological sequelae have also been documented [12].

In patients who present a severe COVID-19 clinical picture, the main sequelae is the development of pulmonar fibrosis. According to a recent metaanalysis, approximately 30% of patients hospitalized with pneumonia due to SARS CoV2 have presented fibrotic changes that persist for the first 12 months after discharge from the hospital [13].

It has been documented that patients with severe forms of COVID-19 presented significant heart injuries, including myocarditis related to infection, with a reduced systolic function and arrhythmias. Myocardial injury has been reported, which may be due to direct damage to the cardiomyocytes, systemic inflammation, myocardial interstitial fibrosis, and hypoxia [14]. Due to significant myocardial injuries in patients with severe clinical symptoms due to COVID-19, the morbidity and lethality of the illness could be high [15-17].

In severe cases of COVID-19, the systemic hyper-inflammatory response could cause long-term cognitive damage, such as, for example, memory loss, attention deficit, slower processing speed associated with cognitive functioning, along with diffuse neuronal loss [18]. Various types of neuropsychiatric clinical signs have also been observed, such as encephalopathy, mood swings, psychosis, neuromuscular dysfunction or demyelinating processes. These may accompany an acute viral infection, or may emerge weeks, months, or even later, post-

infection, in recovered patients [19-21]. According to an electronic follow-up record of 236,379 patients during the first six months following COVID-19 diagnosis, neuropsychiatric complications emerge in 34% of cases, not including cephaea. The most common complications include mood and anxiety disorders and psychoses (24%), neuropathies (2,1%), ischaemic heart disease (2.8%) and dementia (0.67%) [22]. On the other hand, the most frequent neurological symptoms are cephaea and cognitive changes, described in up to 68% and 81% of patients, respectively, with some sort of neurological symptom after week 12 following acute infection [23]. Cognitive changes that are usually reported are lack of concentration, attention, or difficulty planning tasks.

The rapid drop in viral load of patients with COVID-19 infection may reduce the frequency of complications caused by the infection in the following months [24].

The WHO European Observatory on Health Systems and Policies estimates that 10% of infected patients remain symptomatic for at least 12 weeks after infection, resulting in long-term sick leave, leaving sequelae that in 0.8% even last more than a year [25]. A study in Spain, based on Social Security data, shows that COVID caused 1.2 million registered sick leaves by March 2021, and its authors indicate that nearly 100,000 people needed 12 weeks or more to recover from post-COVID sequelae. The casualties were justified by almost 50 different symptoms ranging from fever, shortness of breath, fatigue, anxiety, dizziness or memory loss.

On the other hand, data has been published from the COVERS CAN study conducted in the United Kingdom [25], which carried out serial Magnetic Resonance Imaging (MRI) scanning in a sample of 201 generally-healthy, middle-aged individuals, with COVID-19. The investigators found evidence of mild organ impairment of the heart (32%), lungs (33%), kidneys (12%), liver (10%), pancreas (17%), and spleen (6%) and reported that nearly 70% of the individuals suffered impairment in one or more organs 4 months after the initial symptoms of SARS-CoV2 infection, which was higher than age-matched healthy controls.

5.2. Justification of the study

As previously indicated, the APLICOV-PC proof of concept study demonstrated the antiviral activity of plitidepsin in terms of reducing viral load, inducing recovery, and impact on lymphocyte reconstitution and other inflammatory parameters.

A percentage of patients, which varies between 10 and 25%, continue to show symptoms at 3 months after contracting the SARS CoV2 infection: For some of them this significantly restricts their life, requiring them to take long-term sickness leave from work, and leaving them with sequelae that may continue for more than one year.

With this study, we intend to evaluate whether the treatment with plitidepsin, by attaining a reduction in the viral load and a faster recovery of the patient, could have a relevant impact on the emergence of sequelae resulting from the SARS CoV2 infection.

5.3.Study objectives

Evaluate the incidence of post-COVID morbidity and characterise the complications profile in patients who participated in the APLICOV-PC study.

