7. SCREENING OF PATIENTS

All patients who participated in and received plitidepsin in the APLICOV-PC study are eligible candidates for participating in this extension study. The investigative team will contact the patient to agree a date for the medical visit. The patient will be invited to participate in the study, and be handed the Patient Information Leaflet for the same, along with all additional information related to the study that is necessary for obtaining their informed consent.

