12.2. Sample size

The main objective of the study is to evaluate the incidence of post-COVID morbidity and characterize its profile in patients who participated in the APLICOV-PC study. Given that a total of 45 patients received plitidepsin in said study, of which 3 died as a consequence of the progression of the disease, the maximum number of patients who could participate in the study is limited to 42.

Assuming an average incidence of post-COVID complications of 15%, this study would have a power of 80% for detecting a reduction of 10%: if 3 or less patients presented post-COVID complications, the study would reject the null hypothesis (incidence of post-COVID complications: 15%) and would accept the alternative (5%), with an alpha error of 0.05 (unilateral).

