2.2 Justification of the study

The APLOCOV-PC proof of concept study demonstrated the antiviral activity of plitidepsin in terms of viral load reduction, recovery induction, lymphocyte and other inflammatory parameters reconstitution.

Approximately 10 to 25% of patients with COVID-19 experience symptoms beyond 3 months, resulting in a significant restriction in their everyday lives due to the sequelae of the disease that may persist for a year or more and entail long-term medical leaves.

The aim of this study is to assess whether the treatment with plitidepsin, by attaining a reduction in the viral load and a faster recovery of the patient, could have a relevant impact in preventing the appearance of sequelae resulting from the SARS-CoV-2 infection.

23 Code of the study

E-APLOCOV-PC (AV-APL-A-003-21).

24 Sponsor

Pharma Mar, S.A

25 Design

Multi-site extension study of the APLOCOV-PC clinical study follow-up.

To participate in the study, the patients must have previously participated in the APLOCOV-PC proof of concept study and may have received:

- 1.5 mg of plitidepsin administered as a 1.5-hour infusion, once a day for 3 consecutive days (total dose 4.5 mg).
- 2.0 mg of plitidepsin administered as a 1.5-hour infusion, once a day for 3 consecutive days (total dose 6.0 mg).
- 2.5 mg of plitidepsin administered as a 1.5-hour infusion, once a day for 3 consecutive days (total dose 7.5 mg).

Patients were enrolled after signing informed consent to participate in this extension study.

26 Study Objectives

To evaluate the incidence of post-COVID-19 morbidity and characterize the profile of complications in patients who participated in the APLOCOV-PC study.

27 Endpoints

Incidence of post-COVID-19 complications.

28 Study population

The main objective of the study is to evaluate the incidence of post-COVID-19 morbidity and

characterize the profile of complications in patients who participated in the APLICOV-PC study. The maximum number of patients who can participate in the trial is limited to 42.

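### The rationale and the sample-size rule read as a test of plitidepsin's effect on sequelae, but an uncontrolled cohort in which everyone was treated can only describe incidence, so a low count could be misread as a drug effect.

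*Protocol*

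**What the plan says.** Three places bear on what the study may conclude.

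- **Rationale.** Protocol 5.2 says "With this study, we intend to evaluate whether the treatment with plitidepsin", by lowering viral load and speeding recovery, could matter for the emergence of sequelae. SAP 2.2 puts it as the purpose of the study: "The aim of this study is to assess whether the treatment with plitidepsin" "could have a relevant impact in preventing the appearance of sequelae resulting from the SARS-CoV-2 infection".
- **Formal objective.** Protocol 5.3 reads "Evaluate the incidence of post-COVID morbidity and characterise the complications profile in patients who participated in the APLICOV-PC study". SAP 2.6 says the same. Neither mentions a comparison or a drug effect.
- **Sample size.** Protocol 12.2 notes that 45 patients received plitidepsin and 3 died, so "the maximum number of patients who could participate in the study is limited to 42". It takes 15% as the average incidence of complications, without a source, and claims 80% power at one-sided alpha 0.05 to detect a 10-point reduction to 5%: "if 3 or less patients presented post-COVID complications, the study would reject the null hypothesis" and accept 5%.

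On the population, section 7 says "All patients who participated in and received plitidepsin in the APLICOV-PC study are eligible candidates for participating in this extension study". Sections 7.3 and 7.4 mark randomisation and masking as not applicable. Section 12.1 describes the analysis as mainly descriptive, with exact 95% confidence intervals for relevant categorical variables.

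**The concern.** The rationale asks a causal question: would these patients have had more sequelae without plitidepsin? The design contains no information on that. There is no untreated arm and no matched external cohort. The only planned contrasts are between dose cohorts, between severity groups and with baseline covariates, and none of these supplies an untreated comparator.

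Section 12.2 is where this could do harm. It calls the gap between the observed count and an assumed 15% a reduction, and it tells the reader to accept 5% when the count is low. Read together with 5.2 and SAP 2.2, a count of 3 or fewer invites the conclusion that plitidepsin lowered the incidence. The same count would also be expected if comparable untreated patients had a background rate somewhat below 15%.

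**Working it through.** **Inputs.** N = 42, cut-off 3, null rate 15%, alternative 5%, power 80%, one-sided alpha 0.05 (protocol 12.2). Background rates cited in the protocol: 10–25% with symptoms at 3 months (5.2), and about 30% with fibrotic changes persisting over the first 12 months after discharge among patients hospitalised with pneumonia (5.1). Follow-up in this study: almost 12 months (5.1).

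**Formula.** With X the number of patients with complications, P(X ≤ 3) = Σ C(42, k) p^k (1 − p)^(42 − k), for k = 0 to 3.

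**Step 1: the plan's own figures.**
- At p = 0.15: 0.0011 + 0.0080 + 0.0291 + 0.0685 = 0.107. The stated alpha is 0.05.
- At p = 0.05: P(X ≤ 3) = 0.843. The stated power is 0.80.
- A cut-off of 2 gives alpha 0.038 and power 0.649, so no cut-off at N = 42 meets both targets.

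This failure to reproduce is a separate defect. The present point does not depend on it (step 3).

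**Step 2: how often an inert drug meets the rule.** If plitidepsin does nothing, p is simply the background rate in patients like these.

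| Background rate | P(3 or fewer of 42), no drug effect |
|---|---|
| 10% | 0.384 |
| 15% | 0.107 |
| 20% | 0.021 |
| 25% | 0.003 |
| 30% | 0.0003 |

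The 10%, 25% and 30% rows use rates cited in the protocol, 15% is its benchmark, and 20% is an intermediate value. Across the 10–25% range alone the probability falls from 38% to 0.3%.

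**Step 3: the point survives a correctly sized rule.** With the cut-off lowered to 2, alpha at 15% is 0.038. If the true background were 10%, an inert drug would still meet that rule with probability 0.0120 + 0.0559 + 0.1273 = 0.195. A valid test of 15% remains a test of an assumed number, not of the drug.

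**Step 4: what the count would show descriptively.** 3/42 = 7.1%. The exact (Clopper–Pearson) 95% interval is 1.5% to 19.5%, which contains both 10% and 15%. This is not an artefact of using two sides: the one-sided 95% upper limit is 17.4%, also above 15%.

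**Step 5: is the benchmark matched?** The 10–25% range describes symptoms at 3 months, whereas complications here are counted over almost a year from the last APLICOV-PC visit. No cited rate is shown to match this cohort in both severity and time window.

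**The case against.** The other side has a good deal to say.

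- **The formal objective is already descriptive.** It is stated that way throughout both documents, and the endpoint is incidence. The causal sentences sit under a justification heading and are hedged with 'could'. This stands, and it limits the point to a mismatch between rationale, objective and sample-size rule. It does not remove it: SAP 2.2 still names the treatment's impact as the aim, and 12.2 still equates a low count with a reduction.
- **The SAP carries no 15% test.** SAP section 7 and Tables 11.1.1 and 11.1.2 give counts and percentages only. A reader might infer that a low count is bound to be reported as plitidepsin reducing complications. The documents do not support that; they support only that it could be read so, because 12.2 is in force and no caveat appears anywhere.
- **The low end of the range may not fit these patients.** They were hospitalised, and 87% had moderate to severe disease on entry (5.1). The protocol also cites higher rates, about 30% for fibrotic changes and 34% for neuropsychiatric complications. At 30% an inert drug would almost never meet the rule. A reader might take 0.384 as the false-positive risk; it is one end of a wide range. What stands is the width of that range.
- **Survivor selection.** A reader might infer that excluding the 3 deaths explains a low count as well as a drug effect would. The documents do not support that. Post-COVID complications can be seen only in survivors, and the protocol's cited figures largely describe survivors too. Selection through consent is possible, since refusals are not replaced (8.2), but nothing in the documents lets one size it.

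**Conclusion.** The concern holds as a mismatch between the claim and the design. The study can estimate the incidence and profile of complications in consenting, plitidepsin-treated patients. It cannot attribute a low incidence to plitidepsin, and 12.2 as written permits that reading.

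The size is best given as a range: with no drug effect, the rule is met with probability from 0.384 at a 10% background to 0.0003 at 30%. The conclusion is therefore governed largely by an unsourced benchmark. The figures assume all 42 eligible patients are analysed, independent binomial outcomes and the cut-off of 3 held fixed. The causal limitation itself rests on no arithmetic, only on the absence of a comparator.

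**What to change.** 1. **Protocol 5.2 and SAP 2.2:** reword the purpose to match 5.3, that is, to describe the incidence and profile of post-COVID complications in patients treated with plitidepsin in APLICOV-PC.
2. **Protocol 12.2:** replace the language of detecting a reduction with a comparison against an assumed benchmark. State that rejecting 15% would show only that incidence in the analysed, consenting patients is below that benchmark, and that it is not evidence of a treatment effect.
3. **Reporting:** give the incidence with the exact 95% confidence interval planned in 12.1, and read it against the 10–30% range cited in the protocol, noting the difference in time windows. SAP Table 11.1.1 now shows n (%) only, so the interval needs adding there. Extra benchmark p-values are not needed, because the interval can be set against any rate.

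The cost is wording in three places and one added interval, with no new patients, visits or data. If the documents can no longer be amended, the same wording can govern the final report. The downside is a weaker headline claim.
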